## 6 Administration of Study Treatment

These data are an important part of the safety review, with particular emphasis on infusion-related reactions and symptoms occurring during or within up to 2 hours after the infusion. These reactions and symptoms will be graded according to the DAIDS AE Grading Table.

The administration of study treatment is also an essential element of study conduct. Several summaries, pooled across treatment groups, will be included in the open report or provided to study leadership. Any summaries of adverse events or infusion-related reactions are restricted to the closed report.

**For investigational agents administered as a one-time infusion**, the following statistics will be used to summarize the infusion in each treatment group (active and control):

- Number and percentage of participants receiving complete infusion, partial infusion, infusion paused but resumed for complete infusion, or not infused (comparison by intention-to-treat).
- Number and percentage of participants with infusion-related reactions and symptoms (reported during the infusion or within 2 hours after the infusion), by grade. (Closed report only)
- Number and percentage of participants with an incident AE, SAE, UP or SUSAR on Day 0 during or after the infusion, overall and by oxygen requirement category at time of infusion (oxygen requirement at baseline, unless updated information is available; categories: no supplemental oxygen, < 4 L/min, conventional supplemental oxygen  $\geq$  4 L/min, high-flow oxygen or mechanical ventilation/ECMO). Types of AEs will be summarized by system organ class and by grade. (Closed report only)

- Number and percentage of participants who received:
  - Prior to infusion, medication to prevent infusion reactions, and type of medication
  - During or within 2 hours after infusion, medication to treat infusion reactions, and type of medication (Closed report only)
- Among participants infused, the day of infusion (same day as randomization, next day, > 1 day after randomization), and time between randomization and beginning of infusion (median hours, IQR).
- Among participants receiving full infusion, duration of infusion (median minutes, IQR).
- Time from vial puncture (beginning of preparation of the study agent by the pharmacist) to the end of the infusion, and number and percent of participants for whom the agent-specific time window was exceeded.
- Remdesivir:
  - Number and percent of participants who received (any) remdesivir, and number of days remdesivir was administered: median, IQR, distribution. (Closed report only)
  - Number and percent of participants who received remdesivir prior to the day of randomization, overall and by number of days prior
  - On the day of randomization: Number and percent of participants who received remdesivir prior to the investigational agent; after the investigational agent; no remdesivir.

Treatment groups will be compared by mITT (excluding participants who did not receive any investigational agent/placebo), unless specified otherwise. The treatment comparisons will be performed using the methods described in section 3 for binary and continuous outcomes (stratified CMH test for comparing percentages, and Wilcoxon rank-sum test [or quantile regression for comparing medians], respectively).

Selected summaries will also be provided separately for the two disease severity strata.

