# 1 Introduction

## 1.1 Objective of the Statistical Analysis Plan

The objective of this statistical analysis plan (SAP) is to provide a description of the general analytic strategy and the statistical methods that will be used to analyze the data for the TICO (Therapeutics for Inpatients with COVID-19) Phase III randomized, blinded, controlled, platform trial. This SAP applies to versions 3-5.1 of the TICO protocol. In version 2, two investigational agents are being studied, a SARS-CoV-2 neutralizing monoclonal antibody (nMAb) (Vir-7831) which is being developed by Vir Biotechnology (Vir) (San Francisco, CA) and GlaxoSmithKline (GSK) (Brentford, U.K.), and two nMAbs given sequentially (BRII-196 and BRII-198) which are being developed by Brii Biosciences (Durham, NC and Beijing). In protocol version 3, a third investigational agent is added, AZD7442, which is a combination of two nMAbs by AstraZeneca (Cambridge, U.K.); in version 4.0, MP0420, a DARPin® molecules was added; in version 5.0 (5.1), PF07304814, an antiviral protease inhibitor was added.

Participants are followed for death or re-hospitalization up to month 12 in version 2, and up to month 18 in versions 3, 4, and 5. The nMAbs and MP0420 are given by single infusion, or two sequential infusions for BRII-196 and BRII-198. PF07304814 requires a continuous infusion for 5 days.

The primary objective of the platform trial is to determine whether investigational agents, that are aimed at enhancing the host immune response to SARS-CoV-2 infection, or directly enhancing viral control in order to limit disease progression, are safe and superior to control (e.g., placebo) when given with standard of care (SOC) for the primary endpoint of time to sustained recovery evaluated up to 90 days of follow-up.

In the platform trial, several agents may be investigated in parallel, or staggered with overlapping times; investigational agents may be added or dropped. When more than one agent is being tested concurrently, where possible, participants will be randomly allocated across agents (as well as between the agent and its matched placebo), and the control group is pooled across the concurrently randomized, agent-specific matched placebo groups. Thus, each investigational agent and the corresponding pooled control group form their own randomized trial, and several agents may (at least partially) share their pooled control groups.

This SAP:

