## **1.3 Randomization**

The randomization is described in section 6.1 of the protocol.

Patients will be equally allocated to each investigational agent + SOC or to placebo + SOC. For example, for a study of a single investigational agent, participants will be randomized in a 1:1 ratio to the investigational agent or placebo. If a patient is eligible for two investigational agents and the placebo can be shared, the allocation will be 1:1:1 to investigational agent A, agent B, or placebo. Because the two investigational agents (A and B) may require different placebos

(for example, when infusion volumes differ), the 1:1:1 allocation ratio will be achieved through a two-step randomization procedure: in *step 1*, the participant is randomized 2:1 to “active” versus “placebo”; in *step 2*, the participant is randomized 1:1 to A versus B. With  $k$  agents, this can be viewed as an initial  $k:1$  allocation to “active” versus “placebo”, followed by a second, even allocation to one of the available agents (for example, if a participant was allocated to “placebo” in *step 1*, then the *step 2* allocation will be 1:1 to “matched placebo for A” versus “matched placebo for B”). For the analysis, the concurrent agent-specific placebo groups will be pooled, resulting in a 1:1 allocation ratio for comparing each investigational agent versus the (pooled placebo) control group. If investigational agents are added or dropped, the allocation ratio to active versus placebo will be appropriately modified, and sample size will be recalculated as appropriate.

Randomization will be stratified by study site pharmacy (several clinical sites may share one pharmacy) and severity of disease at entry; the two disease severity strata are defined in section [1.2](#) of this SAP.

If more than one investigational agent is being compared with placebo and they have different contraindications, it is possible that a participant is eligible only for a subset of agents.

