Comparisons will be of each investigational treatment against its control arm. The control arm consists of all participants who were “at risk” of being randomized to the investigational agent but were randomized to a control group instead. This concept is relevant when the randomization includes investigational agents with different eligibility criteria, when agents are introduced into the platform trial at different time points, or randomization to one of the agents is halted temporarily. Formal randomization includes agent-specific matched placebo groups, and the placebo groups will be pooled across agents, but only participants who 1) were eligible for the investigational agent under consideration, and 2) were randomized contemporaneously and at participating sites will be included in the control group for a given agent. At the time of randomization, for each participant, indicator variables will be set that record whether an agent was included in the randomization for that participant (e.g., indicator  $A=1$ , indicator  $B=1$ , indicator  $C=0$  if the participant was eligible to be randomized to agents A and B, but not C). The pooled control group for agent A then consists of all participants who were randomized to (any) placebo, and for whom indicator  $A=1$ .

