## 2 Interim DSMB Reviews: Goals and Format

**Each investigational agent versus control will be reviewed as a separate clinical trial;** separate data reports will be prepared for each investigational agent and the corresponding randomized (pooled) placebo group.

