### 3 Analysis Principles

**Each investigational agent versus control will be treated as a separate clinical trial;** data reports will be for one “target” investigational agent and its corresponding randomized (pooled) control group. Investigational agents will not be directly compared against each other, unless explicitly stated in the agent-specific data analysis plan and agreed upon by all stakeholders. Therefore, in the event that several investigational agents are included in the platform trial in parallel, the pairwise comparisons of each agent versus control will **not** be adjusted for potential inflation of Type I error “due to multiple comparisons”.

Comparisons will be of each investigational treatment against its (pooled) control arm.

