#### **Analysis populations:**

- Comparisons for safety outcomes will be by modified intention-to-treat (mITT). The mITT analysis is restricted to participants who received a complete or partial infusion of the investigational agent/placebo; participants who did not receive any of the investigational agent/placebo are excluded.
- Comparisons for efficacy endpoints will be by intention-to-treat (ITT), unless otherwise stated. If analyses are by ITT, sensitivity analyses by mITT will be carried out for primary outcomes and key secondary outcomes.
- The analysis populations will be reconsidered prior to unblinding with consideration of the number of participants who were not infused, whether reasons for not infusing are independent of the treatment assignment, and the number of participants who have no follow-up data due to withdrawal of consent prior to infusion.

**Pooled control group:** As stated in section 1.3 above, the control arm for any investigational agent will be pooled across the agent-specific control groups for all agents that concurrently participated in the randomization. Specifically, the pooled control group for investigational agent A consists of all participants who might have been randomized to agent A but were randomized

to a placebo group instead. This concept is relevant when a participant is eligible to be randomized to more than one investigational agent, and agents were introduced into the platform trial at different time points or have different eligibility criteria.

In order to identify the pooled control group for each investigational agent correctly, the randomization application is setting indicator variables at the time of randomization for each participant that record whether an agent was included in the randomization (e.g., indicator A=1, indicator B=1, indicator C=0 if the participant was eligible to be randomized to agents A and B, but not C). The pooled control group for agent A then consists of all participants who were randomized to (any) placebo, and for whom indicator A=1.

Therefore, only participants who 1) were eligible for the investigational agent under consideration, 2) were randomized contemporaneously and at participating sites, and 3) were randomized to placebo will be included in the control group for a given agent.

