- AEs, SAEs, and UPs will be classified by MedDRA® system organ class. AEs will be graded for severity according to the *DAIDS AE Grading Table*. Grade 1-4 clinical AEs will be reported at baseline (Day 0 prior to infusion of the investigational agent), Day 0 after the infusion, Days 1-7, and on Days 14 and 28.

The number and percent of participants with AEs will be summarized by day (Day 0 separately prior and after the infusion) and grade, and by system organ class and grade. Comparisons between treatment groups will be for the proportion of participants with AEs of a given grade or higher (i.e., any grade, grade 2+, grade 3+, grade 4). The treatment comparisons will be performed using stratified CMH tests or logistic regression.

- For comparisons by day, the proportion of participants with any grade AEs will be compared for Days 0 (after infusion) through 7, and on Days 14 and 28.
- For comparisons by grade, the proportion of participants who experienced any grade AEs (grade 2+ AEs, etc.) between Day 0 (after the infusion) through Day 7 will be compared.
- For the comparison by system organ class, CMH tests will be performed if the number of participants with AEs is sufficiently large. System organ classes may be split up into MedDRA® preferred terms (PT) for system organ classes where the treatment difference is significant.

Other clinically meaningful AE groupings (beyond system organ class) may be developed by the study team, who are blinded to the treatment effect.

- In addition to any grade AEs through Day 7, grade 3 and 4 clinical AEs are being reported through Day 28. The number and percent of participants with incident grade 3 or 4 AEs through Day 28 will be summarized, overall and by system organ class, and compared between treatment groups using stratified CMH tests. (A grade 3 or 4 AE is considered “incident” if the event was not present at baseline or increased to grade 3 or 4 from grades 1 or 2.)

To illustrate the time course, the incidence of *grade 3 or 4 AEs or death* through Day 28 will be summarized by treatment group using Kaplan-Meier estimates of the cumulative incidence functions (CIF).

- Infusion-related reactions and symptoms during infusion or within 2 hours after infusion of the investigational agent or placebo, and infusion cessation prior to completion will be tabulated and compared between treatment groups; analyses are described in section 6.

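### For one-time-infusion agents, infusion-related items are compared with placebo pooled across agents without regard to infusion regimen, so when concurrent regimens differ the contrast mixes regimen and drug effects.

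*SAP*

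**What the plan says.** **Control group.** SAP section 3 states: "Comparisons will be of each investigational treatment against its (pooled) control arm". The definition is: "The pooled control group for agent A then consists of all participants who were randomized to (any) placebo, and for whom indicator A=1". Section 1.3 sets the limits: "the placebo groups will be pooled across agents, but only participants who 1) were eligible for the investigational agent under consideration", with contemporaneous randomization at participating sites as the second condition. Infusion regimen is not a condition. Section 2 carries this into monitoring: "separate data reports will be prepared for each investigational agent and the corresponding randomized (pooled) placebo group".

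**Regimens.** Section 1.3 explains the two-step randomization this way: "Because the two investigational agents (A and B) may require different placebos", with infusion volume as the example. Step 2 assigns the agent-specific matched placebo. Section 1.1 describes single infusions, two sequential infusions for BRII-196/198, and one longer regimen: "PF07304814 requires a continuous infusion for 5 days".

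**Infusion items.** For one-time-infusion agents, section 6 states that "the following statistics will be used to summarize the infusion in each treatment group (active and control"). The list includes completion, reactions from the start of infusion to two hours after its end, medication for reactions, infusion duration, and time from preparation to end of infusion. Section 6 then plans stratified CMH tests for percentages and Wilcoxon or quantile methods for times. Under section 3 the strata are site pharmacy and disease severity. Section 7 adds that reactions and "infusion cessation prior to completion will be tabulated and compared between treatment groups", referring back to section 6. Neither section names the matched placebo as control, splits control by placebo type, or stratifies by it. Appendices E and G do not change this for AZD7442 or MP0420.

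**The concern.** Pooling is sound for recovery and mortality through Day 90, where the kind of saline infusion given on Day 0 should matter little. The infusion items are different because the regimen helps define them. The reaction window runs until two hours after the infusion ends, so a longer or second infusion gives more time in which a background symptom can be counted. Completion, duration and preparation-to-end time describe the regimen directly.

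Everyone in the agent's arm is assigned that agent's regimen, while the pooled control may be a mixture. If other placebos in the pool carry a higher reaction rate, a true excess can be diluted or hidden. If they carry a lower rate, an excess can appear that the drug did not cause. This bias does not shrink as the trial grows. Section 6 gives these data particular weight in the safety review, and the reaction summaries go to the DSMB in the closed report.

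**Working it through.** **1. Allocation (SAP section 1.3).** With k agents, step 1 allocates k:1 to active versus placebo and step 2 splits evenly.
- Each agent: [k/(k+1)] x (1/k) = 1/(k+1).
- Pooled placebo: 1/(k+1). Agent to pooled placebo is therefore 1:1, as the SAP states, for every k.
- Matched placebo: 1/[k(k+1)]. Agent to matched placebo is k:1. The matched share of the pool is 1/k: 50% for k=2, 33% for k=3.

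**2. Expected difference with no drug effect.** The agent arm has rate pA, the rate under its own placebo. The pool has pA/k + (1 - 1/k)pB. The difference is (1 - 1/k)(pA - pB). It is zero if k=1 or if the placebo rates are equal.

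**3. Size under assumed rates.** The documents give no reaction rates. Assumed: pA=5%, and pB half, equal to or twice pA. The arm size of 500 is from section 1.4. The test is an unstratified two-sided two-proportion z-test at 0.05, standing in for the stratified CMH test.

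| k | pB | Pooled rate | Difference (points) | Apparent risk ratio | Rejection |
|---|---|---|---|---|---|
| 2 | 2.5% | 3.75% | +1.25 | 1.33 | 16% |
| 2 | 5% | 5% | 0 | 1.00 | 5% |
| 2 | 10% | 7.5% | -2.5 | 0.67 | 37% |
| 3 | 2.5% | 3.33% | +1.67 | 1.50 | 26% |
| 3 | 5% | 5% | 0 | 1.00 | 5% |
| 3 | 10% | 8.33% | -3.33 | 0.60 | 56% |

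Worked row (k=2, pB=10%): the average rate is 6.25%, the null SE is sqrt(0.0625 x 0.9375 x 2/500) = 0.0153, and the SE under the actual rates is also 0.0153. Then (0.025 - 1.96 x 0.0153)/0.0153 is about -0.33, which gives 37%.

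Range for k=2: with pA=2%, rejection is 9% (pB=1%) and 17% (pB=4%); with pA=10%, it is 29% (pB=5%) and 67% (pB=20%). Over pA of 2% to 10%, pB of 0.5 to 3 times pA, and k of 2 or 3, it runs from 5% to nearly 100%.

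**4. Masking and precision.** Suppose the drug truly doubles the rate from 5% to 10%.
- Pooled control, equal placebo rates: power 85%.
- Pooled control, pB=10%: the apparent risk ratio is 1.33 (k=2) or 1.20 (k=3), and power is 29% or 15%.
- Matched control: the expected risk ratio stays 2.0, and power is 66% (500 v 250) or 51% (500 v 167).

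At equal variance, the matched-to-pooled SE ratio is sqrt[(1+k)/2]: 1.22 for k=2, 1.41 for k=3.

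**5. Why a crude matched contrast is not enough.** Section 1.3 lets the set of eligible agents differ between participants. Suppose half of the agent arm (n) was eligible for one agent only and half (n) for two. The matched controls number n and n/2, so the single-agent set is 50% of the agent arm but n/(1.5n) = 67% of the controls. Stratifying by eligible-agent set removes this imbalance.

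**The case against.** **A reader might infer that 5-day placebo recipients distort the reaction rates of short-infusion agents, or the reverse.** The documents do not support this. The section 6 list is limited to one-time-infusion agents, so it prescribes no such comparison for PF07304814. Sections 1.1 and 1.3 make shared allocation depend on whether it is possible and whether the placebo can be shared. No passage shows 5-day placebo in a one-time agent's pool. The control definition would allow it, but that is all.

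**The one-versus-two-infusion case is also uncertain.** BRII-196/198 was studied under protocol version 2, while this SAP covers versions 3 to 5.1, and nothing shows its placebo in the AZD7442 or MP0420 pool. No infusion times are given. If one assumes 1-hour infusions given back to back with a single 2-hour tail, the windows are 3 and 4 hours. The null ratios are then about 3/3.5 = 0.86 and 4/3.5 = 1.14, which is modest.

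**Other safeguards exist.** The Day 5 composite, daily adverse events and event listings do not depend on infusion length. Day 0 adverse events are bounded by the calendar day. The harm boundaries in sections 10.1 and 10.3 do not use infusion reactions. The DSMB is unmasked and may request more summaries. A difference in duration between regimens would be self-evident. The time-window check is already agent-specific.

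**Replacing the pooled control has a price.** Precision falls, and an unstratified matched contrast is confounded by eligibility.

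All of this stands. It narrows the point to the regimen-defined items and argues for adding a matched contrast beside the pooled one. It does not remove the gap: where regimens do differ, the plan as written tests these items against a mixture, and it does not say whose time window applies to a control who received another agent's placebo.

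**Conclusion.** The point holds for one-time-infusion agents, for regimen-defined items, and only when concurrently randomized agents (k greater than 1) have different regimens. The items are infusion-related reactions, medication to treat them, completion or cessation, infusion duration and preparation-to-end time. In that situation the pooled contrast remains a valid randomized comparison of assignments, but it does not isolate the drug.

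The bias formula follows from the SAP's own allocation scheme. Its actual size and direction are unknown, because they depend on reaction rates, infusion times and a pool composition that the documents do not give. The figures of 5%, 16% and 37% illustrate what is possible under assumed rates. They do not show that any reported comparison was biased. The primary endpoint and the fixed-window safety outcomes are not affected. This is a cheap improvement.

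**What to change.** In SAP section 6, and in the section 7 item on infusion reactions and cessation, add the following for the regimen-defined items only, whenever concurrent agents' regimens differ:

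- Tabulate the control group by type of placebo received.
- Report the agent versus its own matched placebo beside the pooled comparison, stratified by the set of agents each participant was eligible for. The indicators set at randomization already record this set.
- Interpret these items from the matched contrast, with the pooled result shown next to it.
- State that the time-window check for each control uses the window of the placebo actually received.

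Leave Day 0 adverse events and all other fixed-window safety outcomes on the pooled control.

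The cost is SAP wording and extra table columns, with no new data, since randomization step 2 already assigns the matched placebo. The matched contrast is less precise: SE about 1.22 times for k=2 and 1.41 times for k=3. Splitting one group by placebo type also shows which masked group is control, so these tables belong in the closed report only; little is lost there because section 2 already unmasks the DSMB.
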